10.3 Attribution to agent(s) or procedure

When assessing whether an adverse event (AE) is related to a medical agent(s) medical or procedure, the following attribution categories are utilized:

Definite - The AE is *clearly related* to the agent(s)/procedure.

Probable - The AE is *likely related* to the agent(s)/procedure.

Possible - The AE *may be related* to the agent(s)/procedure.

Unlikely - The AE *is doubtfully related* to the agent(s)/procedure.

Unrelated - The AE *is clearly NOT related* to the agent(s)/procedure.

The following hospitalizations are not considered to be SAEs because there is no “adverse event” (*i.e.*, there is no untoward medical occurrence) associated with the hospitalization:

- Hospitalizations for respite care
- Planned hospitalizations required by the protocol
- Hospitalization planned before informed consent (where the condition requiring the hospitalization has not changed post study drug administration)
- Hospitalization for elective procedures unrelated to the current disease and/or treatment on this trial
- Hospitalization for administration of study drug or insertion of access for administration of study drug
- Hospitalization for routine maintenance of a device (*e.g.*, battery replacement) that was in place before study entry
- Hospitalization, or other serious outcomes for signs and symptoms of progression of the cancer.

10.4 Expedited Reporting Requirements for IND Agents

10.41 Phase 1 and Early Phase 2 Studies: Expedited Reporting Requirements for Adverse Events that Occur on Studies under an IND within 30 Days of the Last Administration of the Investigational Agent/Intervention^{1,2}

FDA REPORTING REQUIREMENTS FOR SERIOUS ADVERSE EVENTS (21 CFR Part 312)

NOTE: Investigators **MUST** immediately report to the sponsor **ANY** Serious Adverse Events, whether or not they are considered related to the investigational agent(s)/intervention (21 CFR 312.64)
An adverse event is considered serious if it results in **ANY** of the following outcomes:

- 1) Death
- 2) A life-threatening adverse event
- 3) An adverse event that results in inpatient hospitalization or prolongation of existing hospitalization for ≥ 24 hours
- 4) A persistent or significant incapacity or substantial disruption of the ability to conduct normal life functions
- 5) A congenital anomaly/birth defect.
- 6) Important Medical Events (IME) that may not result in death, be life threatening, or require hospitalization may be considered serious when, based upon medical judgment, they may jeopardize the patient or subject and may require medical or surgical intervention to prevent one of the outcomes listed in this definition. (FDA, 21 CFR 312.32; ICH E2A and ICH E6).

ALL SERIOUS adverse events that meet the above criteria **MUST** be immediately reported to the sponsor within the timeframes detailed in the table below.

Hospitalization	Grade 1 and Grade 2 Timeframes	Grade 3-5 Timeframes
Resulting in Hospitalization ≥ 24 hrs	7 Calendar Days	24-Hour 3 Calendar Days
Not resulting in Hospitalization ≥ 24 hrs	Not required	

Expedited AE reporting timelines are defined as:

- “24-Hour; 3 Calendar Days” - The AE must initially be reported within 24 hours of learning of the AE, followed by a complete expedited report within 3 calendar days of the initial 24-hour report.
- “7 Calendar Days” - A complete expedited report on the AE must be submitted within 7 calendar days of learning of the AE.

¹Serious adverse events that occur more than 30 days after the last administration of investigational agent/intervention and have an attribution of possible, probable, or definite require reporting as follows:

Expedited 24-hour notification followed by complete report within 3 calendar days for:

- All Grade 3, 4, and Grade 5 AEs

Expedited 7 calendar day reports for:

- Grade 2 AEs resulting in hospitalization or prolongation of hospitalization

² For studies using PET or SPECT IND agents, the AE reporting period is limited to 10 radioactive half-lives, rounded UP to the nearest whole day, after the agent/intervention was last administered. Footnote “1” above applies after this reporting period.

Effective Date: May 5, 2011

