4.0 Test Schedule

4.1 Test schedule for Chemotherapy-Induced Peripheral Neuropathy

Study Visit	1	2	3	4	5	6	7
Study Time Point	Screening /Baseline (Day -30 to Day 1)	Day 1	End of Week 1	End of Week 2 ^c (+3 Days)	End of Week 3	End of Week 4	End of study
CLINICAL ASSESSMENTS							
Informed consent	X						
Inclusion/exclusion criteria	X ^g						
Demographics/ Medical history	X						
Pregnancy testing ^a	X						
Randomization	X						
Dispense Study Product/Placebo		X		X			
Collect questionnaires							X
Adverse event assessment ^b			X	X	X	X	
STUDY TESTING							
EORTC QLQ-CIPN 20 instrument (Appendix I)	X		X	X	X	X	
Global impression of change (Appendix II)			X	X	X	X	
Chemotherapy Induced Peripheral Neuropathy Assessment Tool (Appendix III)	X		X	X	X	X	
Symptom experience diary (Appendix Va & Vb)	X ^d		X ^e	X ^e	X ^e	X ^e	
NCI-CTCAE neuropathy scale ^f (Appendix VI)	X		X	X	X	X	
Cycle = 14 days							
^a For individuals of childbearing potential. Must be done \leq 7 days prior to registration.							
^b Research nurse or clinician to call patient. Including inquiry about skin toxicity and to assess for suicidal thoughts (Appendix IX). Ask the patient if they have missed any doses of the study							

medication and provide education if necessary. Note any other pertinent information that the patient provides.

^c After subject completes week 2 they will turn in completed questionnaire diary and start the next supply of cream within 1-3 days after completing the first 2 weeks, ideally.

^d Appendix Va: System Experience Diary used for baseline assessment. Must be completed prior to application of study medication.

^e Appendix Vb: System Experience Diary used for weekly assessments. Must be completed at the end of each week.

^f To be completed during research nurse or clinician call to patient per Appendix VI.

^g Required Initial Laboratory Values per inclusion criteria 3.19c can be done any time after the patient has completed their chemotherapy and prior to study registration.

5.0 Stratification Factors:

- Gender (Male, Female, or Other)

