10.52 Death

Note: A death on study requires both routine and expedited reporting regardless of causality, unless as noted below. Attribution to treatment or other cause must be provided.

Any death occurring within 30 days of the last dose, regardless of attribution to an agent/intervention under an IND requires expedited reporting within 24-hours.

Any death occurring greater than 30 days with an attribution of possible, probable, or definite to an agent/intervention under an IND requires expedited reporting within 24-hours.

Reportable categories of Death

- Death attributable to a CTCAE term.
- Death Neonatal: A disorder characterized by cessation of life during the first 28 days of life.
- Death NOS: A cessation of life that cannot be attributed to a CTCAE term associated with Grade 5.
- Sudden death NOS: A sudden (defined as instant or within one hour of the onset of symptoms) or an unobserved cessation of life that cannot be attributed to a CTCAE term associated with Grade 5.
- Death due to progressive disease should be reported as **Grade 5 “Neoplasms benign, malignant and unspecified (including cysts and polyps) – Other (Progressive Disease)”** under the system organ class (SOC) of the same name. Evidence that the death was a manifestation of underlying disease (e.g., radiological changes suggesting tumor growth or progression; clinical deterioration associated with a disease process) should be submitted.

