10.62 All other AEs

All other AEs will be addressed during the weekly phone calls with the research nurse or clinician. Patient questionnaire booklets are not collected until the end of the study, therefore, will not be used to collect & document AEs.

Submit via appropriate MCCC Case Report Forms (i.e., paper or electronic, as applicable) the following AEs experienced by a patient and not specified in Section 10.6:

10.621 Grade 2 AEs deemed *possibly, probably, or definitely* related to the study treatment or procedure.

10.622 Grade 3 and 4 AEs regardless of attribution to the study treatment or procedure.

10.623 Grade 5 AEs (Deaths)

10.6231 Any death within 30 days of the patient’s last study treatment or procedure regardless of attribution to the study treatment or procedure.

10.6232 Any death more than 30 days after the patient’s last study treatment or procedure that is felt to be at least possibly treatment related must also be submitted as a Grade 5 AE, with a CTCAE type and attribution assigned.

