16.32 Adverse Event Stopping Rules

Patients who report > grade 2 rash, pain, allergic reaction, or any other > grade 2 side effects attributed to the study medication will stop study drug/placebo and be monitored. Appropriate local care should be administered by the treating physician.

The PI has the right to discontinue this study at any time for reasonable medical or administrative reasons. The DSMB may also terminate study per early stopping rules.

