Appendix IX: Patient Suicidal Thoughts Assessment and Evaluation for Skin Toxicity

Nurse/clinician Phone Call Questions to address regarding suicidal thoughts and potential skin toxicity.

Patients will be asked at the end of each week.

1. Given an abundance of precaution, we want to ask you about whether you have had any thoughts of suicide since starting this protocol?
 - If the answer is 'no', please record.
 - If the answer is 'yes', please record then physician contact is required, and appropriate intervention is to be provided.
2. Do you have skin irritation on your hands and/or feet in the location of the cream application?
3. Do you have any rash, blisters, or open areas of skin in the location of the cream application?
 - Please record responses.
 - If the answer is 'yes' to any of the above two questions, the patient will be asked to come in to be seen by a provider for a skin examination.

Additionally:

4. At the end of weeks 2 and 4, please remind patients to mail in or bring in their questionnaires from the prior 2 weeks.
5. Please note any other pertinent information that the patient provides.

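### The last scheduled adverse-event contact is at week 4, although serious events and deaths stay reportable for 30 days after the last application, and scheduled contact after CBD differs by sequence

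*Combined protocol and SAP*

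**What the plan says.** **Reporting duty.** Section 10.41 covers serious adverse events on studies "under an IND within 30 Days of the Last Administration of the Investigational Agent/Intervention", whether or not they are thought related. On the timing of a report it says: "The AE must initially be reported within 24 hours of learning of the AE". Section 10.52 says: "Any death occurring within 30 days of the last dose, regardless of attribution to an agent/intervention under an IND requires expedited reporting within 24-hours". Section 10.6231 repeats the 30 days for routine reporting of deaths. Footnote 1 to 10.41 and section 10.6232 keep related serious events and related deaths reportable after day 30, with no end date.

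**How events are found.** In 4.1 the adverse-event row is ticked at the ends of weeks 1, 2, 3 and 4 only, with the footnote "Research nurse or clinician to call patient". Visit 7 (end of study) has no date, and its only tick is for collecting questionnaires. Section 10.62 says "All other AEs will be addressed during the weekly phone calls with the research nurse or clinician", and adds: "Patient questionnaire booklets are not collected until the end of the study, therefore, will not be used to collect & document AEs". Appendix IX gives the call script: "Patients will be asked at the end of each week".

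**After week 4.** Section 10.7 treats active monitoring as the test schedule in 4.0 and refers to the Forms Packet for submitting later events. Section 16.32 says that patients with an attributed side effect above grade 2 "will stop study drug/placebo and be monitored", without a duration. Section 7.3 allows the code to be broken once the patient has finished the study and returned the questionnaires, so that the patient may choose to go on using CBD.

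**The concern.** The period in which serious events must be reported is longer than the period in which anyone is scheduled to ask about them. A report is due once the site learns of an event, and after week 4 no planned contact exists through which it would learn of one.

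The crossover makes the gap uneven. Patients on CBD first are still called at weeks 3 and 4, after CBD has stopped. Patients on CBD second have their last call as CBD stops. Section 2.1 lists the side effects of CBD cream against placebo as an aim, and section 2.0 omits a washout partly to see whether effects persist after CBD. For safety, persistence can be seen through scheduled contact in one sequence only. At stake are events that start late, the outcome of events still open at week 4, and any CBD that patients use on their own after unblinding.

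**Working it through.** The plan states no figure for follow-up after CBD, so there is none to reproduce. The check is a day count.

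**Inputs**
- Period 1 is 14 days and period 2 another 14 days (section 7.1).
- The gap between supplies, *g*, is ideally 1 to 3 days (footnote c to 4.1). I use 0, 1 and 3 days, with 0 as a lower bound.
- The last adverse-event call is at the end of week 4 (4.1). I assume that it falls on the last day of period 2.
- The reporting window is 30 days after the last application (10.41, 10.52, 10.6231).
- I assume that the patient uses each cream for its full 14 days.

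**Formulas**
- Last application in period 1 = day 14.
- Last application in period 2 = last call = 14 + *g* + 14 = day 28 + *g*.
- CBD first: scheduled contact after CBD = (28 + *g*) − 14 = 14 + *g* days, leaving 30 − (14 + *g*) = 16 − *g* days without it.
- CBD second: (28 + *g*) − (28 + *g*) = 0 days.
- The 30 days after the last cream of either kind end on day 28 + *g* + 30 = 58 + *g*.

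| Gap *g* (days) | Last call (day) | CBD first: days of contact after CBD | CBD first: days of 30 without contact | CBD second: days of contact after CBD | 30 days after last cream end on day |
|---|---|---|---|---|---|
| 0 | 28 | 14 | 16 | 0 | 58 |
| 1 | 29 | 15 | 15 | 0 | 59 |
| 3 | 31 | 17 | 13 | 0 | 61 |

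Blinded staff would count the window from the last cream of either kind. On that count, scheduled contact is 0 of 30 days in both sequences.

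**What is not touched**
- The primary endpoint is change to week 2, before the crossover.
- In period 1 both arms have 14 days of cream and the same two calls, so the adverse-event comparison there is balanced.
- While CBD is being applied, each sequence is called twice: weeks 1 and 2 for CBD first, weeks 3 and 4 for CBD second.

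The gap therefore concerns only events that begin after CBD stops, or that are still open at the last call.

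**The case against.** The strongest reply is that 30 days is a duty to report, not a promise to look. The clock in 10.41 runs from learning of the event, and nothing there says that patients will be contacted for 30 days. This stands. A reader might infer that the protocol contradicts itself, or that it defines a safety window it cannot observe. The documents support neither: spontaneous reports remain possible and must be acted on. A reader might also express the gap as a share of the reporting period, 30/58 = 52%. That denominator is not the plan's, because related serious events and related deaths stay reportable past day 58 with no end date.

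Second, some follow-up after week 4 is already triggered. Under Appendix IX, a patient who reports skin irritation, rash, blisters or open skin at any call is asked to come in for examination, and a report of suicidal thoughts requires physician contact. Section 16.32 adds monitoring. This also stands, so it would be wrong to say that a reaction open at week 4 cannot be followed. It does not help with an event that starts after that call, and no outcome check is scheduled for other open events.

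Third, the Forms Packet is not among the documents and the consent pages were removed, so instructions to patients on reporting late events may exist. The point is therefore limited to scheduled contact.

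Fourth, Appendix VII describes little toxicity with similar topical products, and nothing in the documents points to reactions that first appear after stopping. That lowers the urgency. The same appendix says that no formal pharmacokinetic studies have been done on this product, so late effects are not ruled out either.

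**Conclusion.** The gap is real but modest. After the end of week 4 (about day 28 to 31) no adverse-event contact is scheduled, while serious events and deaths remain reportable for a further 30 days regardless of attribution. Scheduled contact after the last CBD application is about 14 to 17 days for CBD-first patients and 0 days for CBD-second patients, planned at 20 each. The CBD-first days are spent on placebo cream, so an event then could be a late CBD effect or a placebo-period event.

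A reader might conclude that CBD side effects are under-counted in half the patients. The documents do not support that. Only delayed or unresolved events could be missed, and their number cannot be estimated from the documents.

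The day counts assume full 14-day periods, a supply gap of 0 to 3 days and a week 4 call on the last day of cream. A longer gap would add days to the CBD-first figure only; a later call would add the same number to both. The point calls for a cheap improvement to safety data meant to inform a phase III trial. It does not threaten the pilot's main results.

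**What to change.** Add to 4.1 a separate safety phone call about 30 days after the last application, with the adverse-event row ticked, made by the staff who already make the weekly calls. It should ask about:
- serious adverse events and hospitalisation;
- pregnancy;
- the outcome of any event open at week 4;
- any CBD used on the patient's own initiative, and whether the patient has been unblinded.

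Keep this call distinct from Visit 7. Redating Visit 7 would disturb questionnaire collection and could delay unblinding under 7.3, which depends on study completion. Both should stay at the end of week 4, and 7.3 should make clear that the added call does not postpone unblinding.

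List events found at this call separately from the on-treatment adverse-event comparison, because they may be unblinded or follow self-directed CBD use.

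Section 16.32 gives no duration for its monitoring. It should be reconciled with the test schedule; no duration is proposed here.

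The cost is 40 short calls, one case report form page, and a last contact about 30 days later (about day 58 to 61). Contact after CBD would still be longer in CBD-first patients, at 14 + 30 = 44 to 17 + 30 = 47 days against 30, but both sequences would then be asked about at least the first 30 days after CBD.

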10.42 General reporting instructions

The Mayo IND and/or MCCC Compliance will assist the sponsor-investigator in the processing of expedited adverse events and forwarding of suspected unexpected serious adverse reactions (SUSARs) to the FDA and IRB.

Use Mayo Expedited Event Report form

[REDACTED] or investigational agents or commercial/investigational agents on the same arm.

Non-MCCC Institutions: Submit copies to [REDACTED]

10.43 Reporting of re-occurring SAEs

ALL SERIOUS adverse events that meet the criteria outlined in table 10.41 MUST be immediately reported to the sponsor within the timeframes detailed in the corresponding table. This reporting includes but is not limited to SAEs that re-occur again after resolution.

10.5 Other Required Reporting

10.51 Unanticipated Problems Involving Risks to Subjects or Others (UPIRTSOS)

Unanticipated Problems Involving Risks to Subjects or Others (UPIRTSOS) in general, include any incident, experience, or outcome that meets **all** of the following criteria:

1. Unexpected (in terms of nature, severity, or frequency) given (a) the research procedures that are described in the protocol-related documents, such as the IRB-approved research protocol and informed consent document; and (b) the characteristics of the subject population being studied;
2. Related or possibly related to participation in the research (in this guidance document, possibly related means there is a reasonable possibility that the incident, experience, or outcome may have been caused by the procedures involved in the research); and
3. Suggests that the research places subjects or others at a greater risk of harm (including physical, psychological, economic, or social harm) than was previously known or recognized.

Some unanticipated problems involve social or economic harm instead of the physical or psychological harm associated with adverse events. In other cases, unanticipated problems place subjects or others at increased *risk* of harm, but no harm occurs.

Note: If there is no language in the protocol indicating that pregnancy is not considered an adverse experience for this trial, and if the consent form does not indicate that subjects should not get pregnant/impregnate others, then any pregnancy in a subject/patient or a male patient's partner (spontaneously reported) which occurs during the study or within 120 days of completing the study should be reported as a UPIRTSO.

Mayo Clinic Cancer Center (MCCC) Institutions:

If the event meets the criteria for IRB submission as a Reportable Event/UPIRTSO, provide the appropriate documentation and use the Mayo

Clinic Cancer Center Expedited Event Report form

[REDACTED]
[REDACTED] The Mayo Clinic Compliance Unit will review and process the submission to the Mayo Clinic IRB and work with the IND Coordinator for submission to FDA.

Non-MCCC Institutions:

Submit to your IRB as required by your institutional policies.

Submit copies to [REDACTED]
[REDACTED]

10.52 Death

Note: A death on study requires both routine and expedited reporting regardless of causality, unless as noted below. Attribution to treatment or other cause must be provided.

Any death occurring within 30 days of the last dose, regardless of attribution to an agent/intervention under an IND requires expedited reporting within 24-hours.

Any death occurring greater than 30 days with an attribution of possible, probable, or definite to an agent/intervention under an IND requires expedited reporting within 24-hours.

Reportable categories of Death

- Death attributable to a CTCAE term.
- Death Neonatal: A disorder characterized by cessation of life during the first 28 days of life.
- Death NOS: A cessation of life that cannot be attributed to a CTCAE term associated with Grade 5.
- Sudden death NOS: A sudden (defined as instant or within one hour of the onset of symptoms) or an unobserved cessation of life that cannot be attributed to a CTCAE term associated with Grade 5.
- Death due to progressive disease should be reported as **Grade 5 “Neoplasms benign, malignant and unspecified (including cysts and polyps) – Other (Progressive Disease)”** under the system organ class (SOC) of the same name. Evidence that the death was a manifestation of underlying disease (e.g., radiological changes suggesting tumor growth or progression; clinical deterioration associated with a disease process) should be submitted.

10.53 Secondary Malignancy

- A **secondary malignancy** is a cancer caused by treatment for a previous malignancy (e.g., treatment with investigational agent/intervention, radiation or chemotherapy). A secondary malignancy is not considered a metastasis of the initial neoplasm.
- All secondary malignancies that occur following treatment with an agent under an IND will be reported. Three options are available to describe the event:
 - Leukemia secondary to oncology chemotherapy (e.g., Acute Myelocytic Leukemia [AML])

- Myelodysplastic syndrome (MDS)
- Treatment-related secondary malignancy
- Any malignancy possibly related to cancer treatment (including AML/MDS) should also be reported via the routine reporting mechanisms outlined in each protocol.

